1.3 Schedule of activities (SoA)

The SoA lists all of the assessments when they are performed. All data obtained from these assessments must be supported in the participant's source documentation. The "X" in the table denotes when a study assessment is to be performed and results recorded in the clinical database or received electronically from a vendor. The "S" in the table also denotes when certain study assessment is to be performed. While in this case the result is only captured in the participant's source documentation and do not need to be recorded in the clinical database.

Participants should be seen for all visits/assessments as outlined in the SoA or as close to the designated day/time as possible. A window of +/- 7 days from the scheduled day is acceptable for visits after Visit 1 (Day 1 or Baseline). Missed or rescheduled visits should not lead to automatic discontinuation.

If it is a visit with treatment (Day 1, Day 90, Day 180 and Day 270), all assessments should be performed before study treatment administration. Participants who discontinue from study treatment should continue to attend the following visits as indicated in the SoA. Every effort

should be made to encourage participants who discontinue from study treatment to remain in the study for follow up. Participants who discontinue from study should be scheduled for an Early Exit visit if they agree. This Early Exit visit contains the same assessments of the EOS visit, and is suggested to be scheduled at least 30 days after last injection. If not possible, to set an Early Exit visit as soon as possible is also acceptable. At this final visit, all dispensed investigational product should be reconciled, and the adverse events and concomitant medications not previously reported must be recorded on the CRF.

Participants will have to comply with the following restrictions during the study:

- Fasted for at least 10 hours for all visits to obtain fasting lipids and/or glucose blood samples. If the participant is not fasting at the time of Informed Consent signature, he/she will have to return for a blood draw in a fasting state.
- Must refrain from unaccustomed strenuous physical activity for 48 hours prior to any study visit.

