2.3 Benefit/Risk assessment

In general, the risk of participation in this trial may be minimized by compliance with the eligibility criteria and study procedures, and close clinical monitoring of safety parameters. The risk is further reduced by a minimal duration of placebo-controlled period (core part) of only approximately 6 months. In particular any concern about the theoretical risk to participants randomized to Control Group not being on any LLT during the core part of the study is mitigated by the following: 1) The study population is limited to patients with only low and moderate ASCVD risk, who had not been treated with prior LLT and for whom the investigator had not planned to start LLT in the next 6 months. 2) Lifestyle modification is the first line treatment recommended to these patients in the Chinese Lipid Guidelines, with consideration to add lipid lowering therapy (eg. moderate intensity statin) only if patients can not reach lipid targets with 3~6 months of lifestyle adjustment ([Zhao et al 2016](#)). While in this study, participants randomized to Control Group will only receive placebo treatment for 6 months. 3) Instruction on lifestyle modification is provided to all participants in the study according to clinical guidelines throughout the study participation. 4) Additionally, all participants will receive inclisiran treatment in the extension part. In addition to the potential reduction in LDL-C, the benefit a participant may have by participating in this study is the close monitoring of their condition, the opportunity to learn more about primary hypercholesterolemia and how to reduce future progression to clinical ASCVD and prevention of ASCVD events. In case of new onset of ASCVD events (eg. myocardial infarction, ischemic stroke), which is expected to be very rare in these low/moderate risk patients, investigators and treating physician are encouraged to take any action deemed necessary for the safety of the participants based on clinical standard of care.

Women of child-bearing potential must be informed that taking the study treatment may involve unknown risks to the fetus if pregnancy were to occur during the study, and agree that in order to participate in the study they must adhere to the contraception requirements outlined in the exclusion criteria. If there is any question that the participant will not reliably comply, they should not be entered or continue in the study.

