Participants who discontinue from study treatment should continue to attend the rest of the scheduled visits as indicated in [Section 1.3](#).

Participants who discontinue from study should be scheduled for an Early Exit visit if they agree. This Early Exit visit is suggested to be scheduled at least 30 days after last injection. If not possible, to set an Early Exit visit as soon as possible is also acceptable. The Early Exit visit contains the same assessments of the EOS visit. No data beyond Early Exit visit will be collected in the electronic Case Report Form (eCRF).

Investigators, site staff, participants, and the study team should be blinded to on-treatment lipid measurement results throughout the core part after randomization. Investigators, site staff and

participants should continue to remain blinded to the on-treatment lipid measurement results and original randomized treatment group assignment (inclisiran vs placebo) throughout the study until final database lock.

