6.1.3 Treatment duration

The expected duration of the participant's involvement in the study will be approximately 374 days, which includes a screening period (14 days), a subsequent 180-day double-blind, placebo-controlled treatment period (core part), and a 180-day open label treatment period (extension part).

Participants may be discontinued from the study treatment earlier due to any reasons, at the discretion of the investigator or the participant. They will continue to be followed up in the study until EOS as per Assessment Schedule ([Table 1-2](#)).

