7.1 Discontinuation of study treatment

Discontinuation of study treatment for a participant occurs when study treatment is permanently stopped for any reason (prior to the planned completion of study treatment administration, if any) and can be initiated by either the participant or the Investigator.

The Investigator must discontinue study treatment for a given participant if, he/she believes that continuation would negatively impact the participant's well-being.

Discontinuation from study treatment is required under the following circumstances:

- Participant/guardian decision
- Pregnancy
- Use of prohibited treatment as per recommendations in the prohibited treatment section
- Any situation in which continued study participation might result in a safety risk to the participant
- Following emergency unblinding

- Any laboratory abnormalities that in the judgement of the investigator, taking into consideration the participant's overall status, prevents the participant from continuing participation in the study.

If discontinuation from study treatment occurs, the Investigator should make a reasonable effort to understand the primary reason for the participant's discontinuation from study treatment and record this information.

Participants who discontinue study treatment should NOT be considered withdrawn from the study UNLESS they withdraw their consent **Where possible, they should continue attending site visits for the assessments** indicated in [Section 1.3 Schedule of Activities](#).

If the Participant does not wish to attend any further visits, the participants would return to site for early exit visit. This visit is suggested to be scheduled at least 30 days after last injection. If not possible, to set an EOS visit as soon as possible is also acceptable.

If the participant cannot or is unwilling to attend any visit(s), the site staff should maintain regular telephone contact with the participant, or with a person pre-designated by the participant. This telephone contact should preferably be done according to the study visit schedule.

After discontinuation from study treatment, at a minimum, in abbreviated visits, the following data should be collected at clinic visits or via telephone/email contact:

- New / concomitant treatments
- Adverse Events / Serious Adverse Events

The Investigator must also contact the IRT to register the participant's discontinuation from study treatment.

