8.6.4 Pregnancy

If a female trial participant becomes pregnant, the study treatment should be stopped, and the pregnancy consent form should be presented to the trial participant. The participant must be given adequate time to read, review and sign the pregnancy consent form. This consent form is necessary to allow the Investigator to collect and report information regarding the pregnancy. To ensure participant safety, each pregnancy occurring after signing the informed consent must be reported to Novartis within 24 hours of learning of its occurrence. The pregnancy should be followed up to determine outcome, including spontaneous or voluntary termination, details of the birth, and the presence or absence of any birth defects, congenital abnormalities, or maternal and/or newborn complications.

Pregnancy should be recorded and reported by the Investigator to the Novartis Chief Medical Office and Patient Safety (CMO&PS). Pregnancy follow-up should be recorded on the same form and should include an assessment of the possible relationship to the study treatment any pregnancy outcome. Any SAE experienced during pregnancy must be reported.

After consent is provided, the pregnancy reporting will occur up to one year after the estimated date of delivery.

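### Section 2.3 takes a woman with doubtful contraceptive compliance out of the study, while the general rule in Sections 1.3, 4.1, 6.1.3 and 7.1 stops treatment and keeps follow-up

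*Protocol*

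**What the plan says.** Protocol Section 2.3 requires women of child-bearing potential to follow the contraception rules in the exclusion criteria, and adds: "If there is any question that the participant will not reliably comply, they should not be entered or continue in the study". The protocol separates stopping treatment (7.1) from leaving the study (7.2), and this sentence uses the study term. Because it covers continuing as well as entry, it reaches women already randomized.

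The general rule for participants who stop treatment is different:

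- Section 1.3: every effort "should be made to encourage participants who discontinue from study treatment to remain in the study for follow up".
- Section 4.1: "Participants who discontinue from study treatment should continue to attend the rest of the scheduled visits".
- Section 6.1.3: "They will continue to be followed up in the study until EOS as per Assessment Schedule".
- Section 7.1: "Participants who discontinue study treatment should NOT be considered withdrawn from the study UNLESS they withdraw their consent".

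Pregnancy is on the 7.1 list of required treatment discontinuations. Section 8.6.4 agrees: "If a female trial participant becomes pregnant, the study treatment should be stopped". It then follows the outcome of the pregnancy but does not itself mention scheduled visits; those continue because of 7.1. Doubtful contraceptive compliance is not on the 7.1 list. Exclusion criterion 9 ties the contraception requirement to the period of dosing.

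Section 3.1 handles treatment discontinuation by treatment policy, and Section 9.3.3 relies on data retrieved after discontinuation. Sections 1.1 and 4.1 stop eCRF collection at the Early Exit visit.

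**The concern.** The weaker trigger has the stronger consequence: doubt about contraception ends study participation, while an actual pregnancy ends treatment only. Emergency unblinding (6.3.3) likewise stops treatment and keeps follow-up. A site reading 2.3 literally would exit the woman, and a site reading 7.1 would keep her. Nothing in the protocol settles which is right.

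Two things are at stake under the literal reading. The first is data that the treatment-policy estimand is meant to use: the Day 150 value, and one possible retrieved-dropout record for an imputation model that the SAP uses only when there are enough such records. The second is scheduled observation of women who have already been dosed and whose contraception is in question.

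**Working it through.** The plan gives no figure for this point, so there is nothing to reproduce. The check traces a literal exit through the data rules and then puts a size on it.

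**1. Day 150 LDL-C.** Under SAP Table 2-1 an Early Exit visit is mapped to the next scheduled visit.

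| Literal exit | Day 150 value |
|---|---|
| Before Visit 3 (Day 90), Early Exit visit or not | Missing: an Early Exit value maps to Day 30 or Day 90 |
| After Visit 3, before Visit 4, no Early Exit visit | Missing |
| After Visit 3, before Visit 4, with Early Exit visit | Early Exit value used as Day 150 |
| After Visit 4 | Observed; primary endpoint unaffected |

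On timing: Section 7.2 suggests the Early Exit visit at least 30 days after the last injection and accepts an earlier one. After a Day 90 dose that is from Day 90 + 30 = Day 120. For scheduled visits, Section 1.3 says: "A window of +/- 7 days from the scheduled day is acceptable for visits after Visit 1". That makes Day 143 to Day 157 for Visit 4. An Early Exit value at Day 120 is 143 − 120 = 23 days before that window opens.

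**2. Shift in the inclisiran mean per inclisiran participant lost.** SAP 5.4.1.1 imputes from retrieved dropouts if there are enough and otherwise from a control-based model.

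- Retrieved-dropout branch (first choice): the expected shift is about 0 if retrieved participants respond as she would have. The loss is one observation.
- Control-based branch. From the documents: 100 per arm, and the 58% at the top of the Section 4.3 range, which comes from repeat dosing. Assumed: her Day 150 change would have been −d% with d from 40 to 58, each observed post-baseline value is also −d%, her baseline is at the mean, control mean change is 0, and correlation between visits in controls is a common rho of 0.5 to 0.8. The documents give no single-dose Day 150 figure, so the 40% is an assumption.

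With k post-baseline values observed, the expected imputed change is −d·k·rho/(1 + k·rho). The shift in the arm mean is therefore d/(1 + k·rho)/100 percentage points. Example: d = 58, k = 1, rho = 0.5 gives 58/1.5/100 = 0.39.

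| d | k = 0 | k = 1 (rho 0.5 / 0.7 / 0.8) | k = 2 (rho 0.5 / 0.7 / 0.8) |
|---|---|---|---|
| 40 | 0.40 | 0.27 / 0.24 / 0.22 | 0.20 / 0.17 / 0.15 |
| 50 | 0.50 | 0.33 / 0.29 / 0.28 | 0.25 / 0.21 / 0.19 |
| 58 | 0.58 | 0.39 / 0.34 / 0.32 | 0.29 / 0.24 / 0.22 |

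**3. Effect on the primary test.** Assume a true difference of 40 points and three inclisiran losses with no post-baseline value: 40 − 3 × 0.40 = 38.8. With SE = SD × √(2/100), an assumed SD of 20, 30 or 40 gives SE 2.83, 4.24 or 5.66, and z = 13.7, 9.1 or 6.9. The one-sided 0.025 test needs 1.96.

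**4. SAE reporting window.** Section 8.6.3 runs it to the later of last visit + 30 days and last dose + 90 days. With follow-up to Day 360 it ends on Day 390.

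| Doses given | Exit | Window ends | Shorter by |
|---|---|---|---|
| 1 (Day 1) | by Day 61 | Day 91 | 299 days |
| 2 (Day 90) | by Day 150 | Day 180 | 210 days |
| 3 (Day 180) | by Day 240 | Day 270 | 120 days |
| 4 (Day 270) | by Day 330 | Day 360 | 30 days |

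Each row is the maximum for that number of doses; a later exit shortens the window by less.

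**5. Pregnancy testing.** Section 8.4.5 provides urine tests at study visits after screening, with time points left to Table 1-2. These end at exit. The pregnancy-test rows of that table were not readable in the text available, so the number of tests lost is not counted here.

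**The case against.** Section 2.3 is benefit/risk background and Section 7 is the operative text. None of the sections set against 2.3 names contraceptive non-compliance; they state a general rule for people who stop treatment. Section 7.2 allows study exit for any reason, so 2.3 can be carried out within the plan, and a site that follows 7.1 loses nothing. All of that is correct. But 2.3 is written as an instruction, it is the only text on this case, and 7.2 permits an exit without directing one.

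Four stronger readings are tempting and should not be adopted.

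- *Section 8.6.4 by itself keeps scheduled visits.* It does not. It stops treatment and follows the pregnancy outcome; continued visits come from 7.1.
- *Section 7.1 already covers the case.* Its bullet reads "Any situation in which continued study participation might result in a safety risk to the participant". The risk named in 2.3 is to the fetus, so the bullet is not clearly the route.
- *Stopping doses fully meets the purpose of the rule.* Exclusion criterion 9 points that way, but 2.3 ties contraception to taking part in the study, and Section 4.3 describes an LDL-C effect at Day 180 after one dose. A lasting effect is, if anything, a reason to keep observing her.
- *Pregnancies and related SAEs would go unreported.* Section 8.6.4 requires every pregnancy after consent to be reported, with reporting, once consent is given, up to one year after the estimated delivery date, and it covers SAEs during pregnancy. Section 8.6.3 keeps SAEs suspected to be related reportable after the window closes. What ends is scheduled visits and tests, and routine reporting of other SAEs.

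**Conclusion.** The inconsistency is real and worth correcting, but its consequences are small and arise only where 2.3 is followed literally. The documents do not say how many women would be affected, and the number may be zero.

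For the primary endpoint, each inclisiran participant lost before Day 150 with the value missing moves the arm mean toward placebo by 0.15 to 0.58 points in the control-based branch, under the assumed response, correlation and zero control change, and by about 0 in the retrieved-dropout branch. A reader might infer that the primary result is threatened. It is not: z stays at 6.9 or more with three such losses and an assumed SD as high as 40. The objection on statistical grounds is one of principle, since the sentence discards data that the treatment-policy strategy is designed to collect.

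The clearer cost is safety observation. Scheduled follow-up ends early, and the SAE window closes up to 299 days sooner after one dose or up to 210 days sooner after two, falling to 120 and 30 days after three and four. Confidence is high on the mismatch in wording and lower on whether it would ever matter in practice.

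**What to change.** Two edits to the protocol:

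1. In Section 2.3, replace the second half of the sentence with: *they should not be entered or, if already randomized, should not continue study treatment; scheduled visits and assessments continue under Section 7.1 unless the participant discontinues from the study (7.2) or withdraws consent (7.3).*
2. In Section 7.1, add to the list of required study-treatment discontinuations: *doubtful compliance with the contraception requirements.*

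The second edit is needed because changing 2.3 alone would leave the operative section silent on this trigger.

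The cost is one sentence and one bullet. There are no visits or samples beyond those already scheduled, no change to when dosing stops, and no change to the SAP. A participant may still leave under 7.2 or 7.3.

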3.1 Primary estimands

The estimand is the precise description of the treatment effect and reflects strategies to address events occurring during trial conduct which could impact the interpretation of the trial results (e.g premature discontinuation of treatment).

The clinical question of primary interest is: what is the reduction in LDL-C, quantified by difference of mean percentage change from baseline at Day 150, in Chinese adults with low or moderate ASCVD risk and elevated LDL-C who are not on any lipid-lowering therapy, who receive inclisiran as monotherapy, compared to placebo, regardless of discontinuation from study treatment, if other lipid-lowering therapy were not taken, and where death due to CV or non-CV causes is considered an unfavorable outcome.

The primary estimand is described by the following attributes:

Population: Chinese adults with low or moderate ASCVD risk and elevated LDL-C who are not on any lipid-lowering therapy.

Endpoint: Percentage change from baseline at Day 150 in LDL-C.

Treatments of interest: Inclisiran as monotherapy compared to the use of placebo, regardless of study treatment discontinuation.

Handling of intercurrent events:

- Permanent discontinuation of study treatment will be handled with a treatment policy strategy, keeping treatment labels as assigned at randomization.
- Use of prohibited LLT (PCSK9 monoclonal antibodies taken before Day 150 visit assessment or other LLT taken within 30 days before Day 150 visit assessment) will be treated with a hypothetical strategy of what would happen had those LLT not been taken and those participants behaved like other participants in the same treatment group.
- Participants who died will be handled with a composite strategy, death is considered an unfavorable outcome.

Summary measure: the summary measure to be used is the difference of mean percentage changes.

Complete details on the statistical methods and inference, including missing data handling and sensitivity analyses are provided in [Section 9.3](#).

3.2 Secondary estimands

3.2.1 Secondary estimands for core part

The secondary estimands for core part address the same clinical question as the primary estimand, albeit for different endpoints. They share the same population, intercurrent events, summary measure, as well as the same treatments as the primary estimand. They differ by the definition of the endpoints, these being:

- Absolute change in LDL-C from baseline at Day 150
- Percentage and absolute change in PCSK9, TC, HDL-C, non-HDL-C, ApoB, ApoA-1, Lp(a) and TG from baseline at Day 150

The statistical methods and inference approaches are described in Section 9.4.

3.2.2 Secondary estimands for extension part

The clinical question of interest in extension part is: what is the reduction in LDL-C, quantified by mean percentage or absolute change from baseline at Day 330, in Chinese adults with low or moderate ASCVD risk and elevated LDL-C who are not on any lipid-lowering therapy, who receive inclisiran as monotherapy, regardless of discontinuation from study treatment, if other lipid-lowering therapy were not taken, and where death due to CV or non-CV causes is considered an unfavorable outcome.

The secondary estimand for extension part is described by the following attributes:

Population: Chinese adults with low or moderate ASCVD risk and elevated LDL-C who are not on any lipid-lowering therapy.

Endpoint: Percentage or absolute change from baseline at Day 330 in LDL-C for inclisiran group.

Treatments of interest: Inclisiran as monotherapy, regardless of study treatment discontinuation.

Handling of intercurrent events:

- Permanent discontinuation of study treatment will be handled with a treatment policy strategy, keeping treatment labels as assigned at randomization.
- Use of prohibited LLT (PCSK9 monoclonal antibodies taken before Day 330 visit assessment or other LLT taken within 30 days before Day 330 visit assessment) will be treated with a hypothetical strategy of what would happen had those LLT not been taken and those participants behaved like other participants in the same treatment group.
- Participants who died will be handled with a composite strategy, death is considered an unfavorable outcome.

Summary measure: the summary measure to be used is the mean percentage or absolute change.

Complete details on the statistical methods and inference, including missing data handling and sensitivity analyses are provided in [Section 9.4](#).

4 Study design

